## 2 STUDY RATIONALE

VTE is one of the leading causes of maternal morbidity and mortality. In efforts to decrease rates of VTE, there is an increased emphasis on administering pharmacologic thromboprophylaxis for antepartum patients with prolonged hospitalizations. Due to physiological changes of pregnancy that may alter the metabolism of unfractionated heparin, it is suspected that dosing of pharmacologic thromboprophylaxis may need to be altered. ACOG's current recommendation is to consider gestational age-based dosing of unfractionated heparin for hospitalized pregnant patients rather than standard dosing. However, there are no prior studies assessing the potential effects of higher dosing. Potential effects of higher dosing include limited receipt of neuraxial anesthesia, increased administration of general anesthesia, delayed time to delivery, and increased bleeding risk. We propose this study to provide a direct comparison of gestational age-based unfractionated heparin dosing to standard dosing of unfractionated heparin for pharmacologic thromboprophylaxis of hospitalized antepartum patients.

For our primary objective, we hypothesize that compared to standard dosing, gestational age-based dosing for VTE prophylaxis is associated with higher rates of elevated aPTT values, a surrogate marker of ineligibility for neuraxial anesthesia. For our additional exploratory objectives, we hypothesize that there will be no significant difference in achieving goal anti-Xa levels (0.2-0.5 IU/mL) between standard dosing and gestational age-based dosing and that particular characteristics (e.g., increased eGFR and higher BMI) are associated with elevated aPTT values with unfractionated heparin administration.

ACOG Practice Bulletin No.123. Thromboembolism in Pregnancy. *Obstet Gynecol* 2011;118:718-729.

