#### **3.2 Secondary Objectives**

The secondary objective of this study is to evaluate pharmacokinetics and pharmacodynamics of unfractionated heparin in pregnancy.

- a) Determine the frequency of adjusted unfractionated heparin dosing based on elevated aPTT values and assess maternal characteristics associated with elevated aPTT values.
- b) Determine the appropriate dosing of unfractionated heparin for pharmacologic thromboprophylaxis of hospitalized antepartum patients (anti-Xa levels within prophylactic goal range, normal aPTT).

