## **4 STUDY DESIGN**

### **4.1 Study Overview**

This is a single center, open-label, non-placebo-controlled, randomized trial of gestational age-based dosing and standard dosing of unfractionated heparin for pharmacologic thromboprophylaxis of antepartum patients hospitalized for at least 72 hours. 46 (23 in arm 1 and 23 in arm 2) subjects are planned.

Screening data will be reviewed to determine subject eligibility. Subjects who meet all inclusion criteria and none of the exclusion criteria will be recruited for the study. Each subject will be assigned to receive one of two dosing of unfractionated heparin. Subjects will be assigned to the doses in random order.

The following treatment regimens will be used:

- ARM 1 (Control Arm)
  - o Standard dosing: 5,000 units subcutaneous unfractionated heparin every 12 hours
- ARM 2
  - o Gestational age-based dosing:
    - 1st trimester (< 14 weeks of gestation): 5,000 units subcutaneous unfractionated heparin every 12 hours
    - 2nd trimester (14-28 weeks of gestation): 7,500 units subcutaneous unfractionated heparin every 12 hours
    - 3rd trimester ( $\geq$  28 weeks of gestation): 10,000 units subcutaneous unfractionated heparin every 12 hours

Patients will receive serial lab measurements after 2nd dose, 4th dose, 10th dose, and then weekly to monitor. Dosing will be adjusted based on aPTT values (APPENDIX 1).

Total duration of subject participation will be throughout the patient's inpatient hospitalization until they undergo delivery or discharge. Total duration of the study is anticipated to be approximately 18 months.

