## **8 STUDY TREATMENTS**

### **8.1 Method of Assigning Subjects to Treatment Groups**

46 eligible patients will be randomly assigned to standard dosing of unfractionated heparin or gestational age-based dosing of unfractionated heparin in a 1:1 ratio. They will immediately be allocated to their designated arm and this will be documented in their prenatal record. The medical team will be notified of the patient's designated arm and then place the order for unfractionated heparin.

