### **11.4 Analysis of Secondary Endpoints**

Comparison of maternal demographics, baseline characteristics, additional maternal outcomes, and neonatal outcomes between the two groups will be analyzed using Student's t-test for parametric data, Wilcoxon signed-rank test for nonparametric data, and Chi-squared or Fisher's exact test for comparison of proportions. Descriptive statistics will be performed to summarize which dose resulted in a normal aPTT value and anti-Xa within goal range. Multivariate logistic regression analysis will be performed to determine which factors were associated with an elevated aPTT value. Statistical significance will be set at a p-value of  $< 0.05$  or 95% confidence interval not overlapping.

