### **11.5 Sample Size and Randomization**

Based on an informal/pilot review of antepartum admissions at our institution receiving gestational age-based dosing of unfractionated heparin, 40% of patients and an elevated aPTT

value. Assuming 40% of patients receiving gestational age-based dosing and 3% receiving standard dosing had elevated serum aPTT values, a sample size of 18 women in each dosing group would have 80% power (alpha = 0.05) to demonstrate a significant difference in our primary outcome of evaluating the proportion of women with elevated aPTT values after heparin administration. We increased the sample size by 25% to account for post-randomization drop-out or lab sampling errors. We plan to recruit 46 patients.

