Title of Study: Heparin Prophylaxis Dosing for Antepartum Hospitalizations (HEPDOSE)

NCT Number: NCT04635839

Document Date: June 27, 2022

Document: Statistical Analysis Plan

Traditional univariate analysis was performed for our primary and secondary outcomes with Chi-square or Fisher exact test for categorical variable and t-test or Wilcoxon rank-sum test for continuous variables. A logistic regression analysis was performed to further assess the association of elevated aPTT with gestational age-based dosing of unfractionated heparin relative to standard dosing. We also performed a multivariate logistic regression to adjust for confounders. Confounders included in the model were a priori covariates that potentially could affect the response to unfractionated heparin along with baseline characteristics from our univariate analyses comparing study arm groups that had a p value < 0.2. Via a stepwise regression, none of the variable demonstrated a significant effect on our primary outcome. However, for our final model we elected to adjust for creatinine and obesity based on clinical relevance and a priori knowledge of these factors being potential confounders that may not have been detected in our study cohort due to the small sample size.

Statistical significance was defined as a p-value of < 0.05 or non-overlapping 95% confidence intervals (CI). All analyses were conducted using Statistical Analysis Software (SAS), version 9.4 (Copyright 2013, SAS Institute, Inc. Cary, NC).

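### With about 8 to 10 expected events, the logistic regression for maternal characteristics (objective 3.2(a)) has low power for all but strong factors; add a linear model of aPTT in seconds beside it.

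*Protocol*

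**What the plan says.** Protocol section 3.2, objective (a), asks for two things: how often dosing is adjusted, and to "assess maternal characteristics associated with elevated aPTT values". Section 2 gives the hypothesis behind the second part, among the additional exploratory objectives: that "particular characteristics (e.g., increased eGFR and higher BMI) are associated with elevated aPTT values".

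Section 11.4 gives the method in one sentence: "Multivariate logistic regression analysis will be performed to determine which factors were associated with an elevated aPTT value". It names no covariates, sets no limit on model size and specifies no small-sample method. Section 11.5 sizes the trial on the comparison of arms alone.

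The SAP, written in the past tense, fits a multivariable logistic model to adjust the arm effect. Candidates were a priori covariates plus baseline characteristics that differed between arms at p < 0.2. It reports: "Via a stepwise regression, none of the variable demonstrated a significant effect on our primary outcome". The final model nevertheless adjusts for creatinine and obesity on clinical grounds, and the SAP says that such effects may have gone unseen because the cohort was small.

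Sections 10.1 to 10.5 collect aPTT at baseline, 6 hours after dose 2, 2 and 6 hours after dose 4, 6 hours after dose 10, and weekly after that. Neither document plans to model these values in seconds for this objective.

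**The concern.** The sample size supports one comparison with a very large assumed difference. The search for maternal factors uses the same few events, split across several covariates, after each measured aPTT has been reduced to above or below 36.2 seconds. With so few events, a non-significant factor may be unrelated to aPTT or merely undetectable, and a factor that survives selection may be noise. The p < 0.2 screen does not help: it compares the arms, so it picks out baseline imbalance rather than association with aPTT. At stake is whether the trial can say anything useful about BMI and renal function, the two characteristics that section 2 names.

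**Working it through.** **Inputs.** Event rates come from section 11.5: "Assuming 40% of patients receiving gestational age-based dosing and 3% receiving standard dosing had elevated serum aPTT values". Evaluable women: 18 per arm (section 11.5). Recruited: "46 (23 in arm 1 and 23 in arm 2) subjects are planned" (section 4.1). The documents give no effect size for any maternal factor, so the correlations, odds ratios and covariate counts below are assumptions.

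**The plan's own figure.** Two-sided, pooled normal approximation, mean rate 0.215:

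n = [1.96 × √(2 × 0.215 × 0.785) + 0.8416 × √(0.40 × 0.60 + 0.03 × 0.97)]² / 0.37² = (1.139 + 0.437)² / 0.1369 ≈ 18.1.

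Eighteen per arm gives 79.7% power, which agrees with the stated 80%. Then 18 × 1.25 = 22.5, rounded up to 23 per arm, or 46.

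**Events available to the regression.**
- 18 per arm: 18 × (0.40 + 0.03) = 7.7, of which 18 × 0.03 = 0.5 in the standard arm.
- 23 per arm: 23 × 0.43 = 9.9, of which 0.7 in the standard arm.
- Chance of no standard-arm event: 0.97^18 = 58%; 0.97^23 = 50%. That arm then tells the logistic model nothing about which women are elevated.

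**Power at within-arm correlation 0.4.** Simulation: aPTT equals an arm shift plus the factor plus normal noise, cut so that 40% and 3% exceed the threshold. Ranges are over repeated simulations; the lowest linear figures use five terms.

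| Analysis | 18 per arm | 23 per arm |
|---|---|---|
| Logistic, Wald | 17-19% | 29-33% |
| Logistic, likelihood ratio | 28-37% | 37-45% |
| Linear, aPTT in seconds | 59-70% | 76-82% |

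The linear row can be checked by hand with Fisher's z, adjusting for arm. Power ≈ Φ(atanh(r) × √(N − 4) − 1.96).
- r = 0.4, N = 36: 0.4236 × 5.657 − 1.96 = 0.44, so 67%.
- r = 0.4, N = 46: 0.4236 × 6.481 − 1.96 = 0.79, so 78%.
- r = 0.3, N = 36: 0.3095 × 5.657 − 1.96 = −0.21, so 42%.
- r = 0.3, N = 46: 0.3095 × 6.481 − 1.96 = 0.05, so 52%.

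Simulation at r = 0.3 gives 35-54%, again lowest with five terms.

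**Larger logistic models.** With arm plus 2 to 8 covariates and 36 to 46 women, Wald power for one factor is 2-27% at an odds ratio of 2 per SD and 4-52% at 3. Likelihood-ratio power is higher, but that test's type I error is 6.5-17.5% rather than 5%. With 8 covariates, complete separation occurs in 4-51% of runs.

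**Selection (forward, entry at 0.05).** A true factor with odds ratio 2 per SD enters in 28-35% of runs; with 3, in 51-67%. At least one null factor enters in about 5-7% of runs with 2 candidates, 19-24% with 5 and 31-37% with 8.

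**The case against.** Four points weigh on the other side.

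- **The SAP does not claim that there is no association.** It follows the null result with a caution about sample size and keeps creatinine and obesity in the model. A reader might take the stepwise sentence as a finding of no effect; the documents do not support that. What remains is that the caution comes with no estimates, no intervals and no better-powered analysis.
- **The aim is modest.** Section 2 calls the hypothesis exploratory, it is only half of objective 3.2(a), and no power is claimed for it. This stands, and it limits how much the point matters.
- **The objective concerns elevated values.** The 36.2-second cut is the surrogate for neuraxial eligibility, and section 5.1 assesses it at several times. A linear model at one time answers a related but different question. This stands, so it should be added and not substituted.
- **The linear model is no cure.** At correlation 0.3 it does little better than a coin toss, and no document supports 0.4. This also stands.

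A reader might also suppose that BMI was reduced to obesity yes or no for this objective. The SAP mentions obesity only as an adjuster in the final model for the arm effect; it does not say how BMI entered the stepwise step.

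**Conclusion.** The point holds as a cheap improvement to an exploratory part of a secondary objective. About 8 to 10 events, nearly all in one arm, give the logistic model low power for all but strong factors. At an assumed correlation of 0.4 it detects a factor about 20-33% of the time by Wald and 28-45% by likelihood ratio, against about 60-80% for a linear model on data already collected. Neither a null result nor a selected factor is informative.

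It would be tempting to say that the regression finds nothing almost whatever is true. The figures do not support that: with two covariates and all 46 women, Wald power reaches 52% at an odds ratio of 3 per SD and 67% at 4, and selection sometimes returns a factor that is not real.

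The event count rests on the planning rates, and the documents give no source for the 3%. If the standard-arm rate were 10-20%, events would be 18 × 0.50 = 9 to 23 × 0.60 = 14, still few. The linear figures assume roughly normal aPTT, logged if skewed, and a linear effect of the factor. The randomised comparison of arms is not affected.

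**What to change.** For the maternal-characteristics part of 3.2(a), add a linear model of aPTT in seconds (log if skewed) at 6 hours after dose 2, the first on-treatment sample and taken before any aPTT-driven dose change.

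- **Covariates, all fixed in advance:** arm, baseline aPTT, continuous BMI, continuous creatinine or eGFR, and gestational age with an arm-by-gestational-age term (or a term for assigned dose). The last is needed because gestational age sets the dose in arm 2 only, so an additive term alone would mix dose with physiology.
- **No stepwise step and no p < 0.2 screen.** Report every coefficient with its 95% confidence interval.
- **Keep the analysis of values above 36.2 seconds as support,** preferably Firth-penalised logistic regression with a short fixed covariate list.
- **Do not read a null as absence of association.**

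The cost is SAP wording and one regression on data already collected. With these six terms and an intercept, 36 − 7 = 29 to 46 − 7 = 39 residual degrees of freedom remain. Because the SAP already reports a stepwise result, the added model should be labelled post hoc if outcome data have been seen. The downside is that it describes mean aPTT at one time, not ever exceeding 36.2 seconds, and modest associations would still often be missed.

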### **11.5 Sample Size and Randomization**

Based on an informal/pilot review of antepartum admissions at our institution receiving gestational age-based dosing of unfractionated heparin, 40% of patients and an elevated aPTT

value. Assuming 40% of patients receiving gestational age-based dosing and 3% receiving standard dosing had elevated serum aPTT values, a sample size of 18 women in each dosing group would have 80% power (alpha = 0.05) to demonstrate a significant difference in our primary outcome of evaluating the proportion of women with elevated aPTT values after heparin administration. We increased the sample size by 25% to account for post-randomization drop-out or lab sampling errors. We plan to recruit 46 patients.

## **12 ADVERSE EXPERIENCE REPORTING AND DOCUMENTATION**

### **12.1 Adverse Events**

An adverse event (AE) is any untoward medical occurrence in a clinical investigation of a patient administered a pharmaceutical product and that does not necessarily have a causal relationship with the treatment. An AE is therefore any unfavorable and unintended sign (including an abnormal laboratory finding), symptom or disease temporally associated with the administration of an investigational product, whether or not related to that investigational product. An unexpected AE is one of a type not identified in nature, severity, or frequency in the current Investigator's Brochure or of greater severity or frequency than expected based on the information in the Investigator's Brochure.

The Investigator will probe, via discussion with the subject, for the occurrence of AEs during each subject visit and record the information in the site's source documents. Adverse events will be recorded in the patient CRF. Adverse events will be described by duration (start and stop dates and times), severity, outcome, treatment and relation to study drug, or if unrelated, the cause.

#### **AE Severity**

The National Cancer Institute's Common Terminology Criteria for Adverse Events (CTCAE) Version 3.0 should be used to assess and grade AE severity, including laboratory abnormalities judged to be clinically significant. The modified criteria can be found in the study manual. If the experience is not covered in the modified criteria, the guidelines shown in Table 1 below should be used to grade severity. It should be pointed out that the term "severe" is a measure of intensity and that a severe AE is not necessarily serious.

**Table 1. AE Severity Grading**

Severity (Toxicity Grade)	Description
Mild (1)	Transient or mild discomfort; no limitation in activity; no medical intervention or therapy required. The subject may be aware of the sign or symptom but tolerates it reasonably well.
Moderate (2)	Mild to moderate limitation in activity, no or minimal medical intervention/therapy required.
Severe (3)	Marked limitation in activity, medical intervention/therapy required, hospitalizations possible.
Life-threatening (4)	The subject is at risk of death due to the adverse experience as it occurred. This does not refer to an experience that hypothetically might have caused death if it were more severe.

#### **AE Relationship to Study Drug**

The relationship of an AE to the study drug should be assessed using the following the guidelines in Table 2.

**Table 2. AE Relationship to Study Drug**

Relationship to Drug	Comment
Definitely	Previously known toxicity of agent; or an event that follows a reasonable temporal sequence from administration of the drug; that follows a known or expected response pattern to the suspected drug; that is confirmed by stopping or reducing the dosage of the drug; and that is not explained by any other reasonable hypothesis.
Probably	An event that follows a reasonable temporal sequence from administration of the drug; that follows a known or expected response pattern to the suspected drug; that is confirmed by stopping or reducing the dosage of the drug; and that is unlikely to be explained by the known characteristics of the subject's clinical state or by other interventions.
Possibly	An event that follows a reasonable temporal sequence from administration of the drug; that follows a known or expected response pattern to that suspected drug; but that could readily have been produced by a number of other factors.
Unrelated	An event that can be determined with certainty to have no relationship to the study drug.

## **12.2 Serious Adverse Experiences (SAE)**

An SAE is defined as any AE occurring at any dose that results in any of the following outcomes:

- death
- a life-threatening adverse experience
- inpatient hospitalization or prolongation of existing hospitalization
- a persistent or significant disability/incapacity
- a congenital anomaly/birth defect

Other important medical events may also be considered an SAE when, based on appropriate medical judgment, they jeopardize the subject or require intervention to prevent one of the outcomes listed.

### **12.2.1 Serious Adverse Experience Reporting**

Study sites will document all SAEs that occur (whether or not related to study drug) per [UCLA OHRPP Guidelines](#). The collection period for all SAEs will begin after informed consent is obtained and end after procedures for the final study visit have been completed.

In accordance with the standard operating procedures and policies of the local Institutional Review Board (IRB)/Independent Ethics Committee (IEC), the site investigator will report SAEs to the IRB/IEC.

## **13 DISCONTINUATION AND REPLACEMENT OF SUBJECTS**

### **13.1 Early Discontinuation of Study Drug**

A subject may be discontinued from study treatment at any time if the subject or the investigator feels that it is not in the subject's best interest to continue. The following is a list of possible reasons for study treatment discontinuation:

- Subject withdrawal of consent (or assent)
- Subject is not compliant with study procedures
- Adverse event that in the opinion of the investigator would be in the best interest of the subject to discontinue study treatment
- Protocol violation requiring discontinuation of study treatment
- Lost to follow-up
- Sponsor request for early termination of study

If a subject is withdrawn from treatment due to an adverse event, the subject will be followed and treated by the Investigator until the abnormal parameter or symptom has resolved or stabilized.

All subjects are free to withdraw from participation at any time, for any reason, specified or unspecified, and without prejudice.

Reasonable attempts will be made by the investigator to provide a reason for subject withdrawals. The reason for the subject's withdrawal from the study will be specified in the subject's source documents. Refer to **Section 10** for early termination procedures.

### **13.2 Withdrawal of Subjects from the Study**

A subject may be withdrawn from the study at any time if the subject or the investigator feels that it is not in the subject's best interest to continue.

All subjects are free to withdraw from participation at any time, for any reason, specified or unspecified, and without prejudice.

Reasonable attempts will be made by the investigator to provide a reason for subject withdrawals. The reason for the subject's withdrawal from the study will be specified in the subject's source documents. Refer to **Section 10** for early termination procedures.

### **13.3 Replacement of Subjects**

Subjects who withdraw from the study treatment will not be replaced.

## **14 PROTOCOL VIOLATIONS**

A protocol violation occurs when the subject or investigator fails to adhere to significant protocol requirements affecting the inclusion, exclusion, subject safety and primary endpoint criteria. Protocol violations for this study include, but are not limited to, the following:

- Failure to meet inclusion/exclusion criteria
- Use of a prohibited concomitant medication

Failure to comply with Good Clinical Practice (GCP) guidelines will also result in a protocol violation. The principal investigators will determine if a protocol violation will result in withdrawal of a subject.

When a protocol violation occurs, it will be discussed with the investigator and a Protocol Violation Form detailing the violation will be generated. This form will be signed by a Sponsor representative and the Investigator. A copy of the form will be filed in the site's regulatory binder and in the Sponsor's files.

